#### **2.8.4.2 ECHO Data handling**

ECHO data will be analyzed based on local reported results. The summaries will include all ECHO assessments performed no later than 30 days after the last date of study drug. All ECHO assessments will be listed, and those collected later than 30 days after study drug discontinuation will be flagged in the listing.

The same modality (ECHO or MUGA) for determining cardiac scan data (e.g., left ventricular ejection fraction (LVEF)) should be used to follow a patient throughout the study. The absolute change from baseline values will not be calculated for any patients where the post-baseline value was determined by a cardiac scan modality that is different than the one used to determine baseline value.

#### **ECHO Data analysis**

Absolute change from baseline in LVEF will be summarized at each scheduled assessment time and by worst case post-baseline. Only the post-baseline assessments that used the same method (ECHO or MUGA) as the baseline assessments will be used to derive the change from baseline.

The **absolute change from baseline** will be categorized as follows:

- Any increase
- No change
- Any decrease:
  - 0 - <10% decrease
  - 10 - <20% decrease
  - ≥20% decrease
- ≥10% decrease and ≥ Lower Limit Normal (LLN)
- ≥10% decrease and < LLN

- $\geq 20\%$  decrease and  $\geq$  LLN
- $\geq 20\%$  decrease and  $<$  LLN

A listing of all LVEF assessments will be provided including patient level details of absolute change from baseline. Assessments collected outside of on-treatment period will be flagged.

### 2.8.5 Vital signs

The following parameters will be collected: height (cm), weight (kg), body temperature ( $^{\circ}\text{C}$ ), heart rate (beats per minute), respiration rate (breathes/min), systolic and diastolic blood pressure (mmHg).

#### Data handling

Vital signs collected on treatment will be summarized by scheduled visit. Values measured outside of on treatment period will be flagged in the listings.

The baseline blood pressure is the average of the systolic and average of the diastolic measurements.

#### Data analysis

For analysis of vital signs the clinically notable vital sign criteria are provided in Table 2-9.

**Table 2-9 Clinically notable changes in vital signs**

Vital sign (unit)	Clinically notable criteria	
	above normal value	below normal value
Weight (kg)	increase $> 10\%$ from Baseline	decrease $> 10\%$ from Baseline
Systolic blood pressure (mmHg)	$\geq 180$ with increase from baseline of $\geq 20$	$\leq 90$ with decrease from baseline of $\geq 20$
Diastolic blood pressure (mmHg)	$\geq 105$ with increase from baseline of $\geq 15$	$\leq 50$ with decrease from baseline of $\geq 15$
Body temperature	$\geq 38.5$	$\leq 35.0$

The number and percentage of patients with notable vital sign values (high/low) will be presented as described in [Section 2.8](#). Shift tables for vital sign values will also be presented.

Descriptive statistics (mean, median, standard deviation, minimum and maximum) will be tabulated for baseline, at each post-baseline time point and changes from baseline at each post-

baseline time point for each vital sign measure. For each parameter, only patients with a value at both baseline and post baseline (on treatment) will be included.

A listing of all vital sign assessments will be produced by cohorts and notable values will be flagged. In the listing, the assessments collected outside of on-treatment period will be flagged.

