### 1.1 Study design

This is a 4-part (Part A, Part B, Part C and Part D), Phase I/IIa, multi-center, open label, study in pediatric subjects with refractory or recurrent tumors.

**Part A** will be a pharmacokinetically driven limited dose escalation (i.e., 0.0125, 0.025 and 0.04 mg/kg/day) in subjects and will include an expansion for safety, tolerability, and pharmacokinetics (PK) in three age ranges (1 month to <2years, 2 to ≤12 years, and over 12 years of age). The primary goal of Part A is to establish the toxicity profile, PK, and recommended Phase 2 dose (RP2D) of trametinib in each age cohort. Approximately 18 subjects will be accrued to the dose escalation phase and 18 subjects to the age expansion phase.

**Part A extension** will be an age-specific dose exploration in up to 12 subjects aged 1 month to < 6 years old. Preliminary PK analysis of pediatric patients in this current study suggests that for patients < 6 years old, an intermediate dose (i.e., 0.032 mg/kg/day) may increase the proportion of these patients who achieves exposures similar to adults. The goal of this additional dose exploration is to establish the safety, tolerability, PK and further refine the RP2D of trametinib in this younger age cohort.

**Part B** will be a tumor cohort expansion part of the study to further evaluate the safety, tolerability, and preliminary clinical activity of trametinib at the dose determined in Part A in tumor-specific pediatric populations. Disease cohorts are selected based on current data of proto-oncogene RAS (Ras)/ mitogen-activated protein kinase (MAPK) activation in childhood solid tumors. At least forty subjects are planned for Part B, 10 subjects in each of 4 disease cohorts.

- B1: Refractory or relapsed neuroblastoma
- B2: Recurrent or unresectable low grade gliomas associated with BRAF tandem duplication with fusion, or NF-1 subjects with gliomas, not suitable for the NF-1 with PN cohort
- B3: Neurofibromatosis Type -1 associated plexiform neurofibromas that are unresectable and medically significant.

- B4:BRAF V600 mutant tumors

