**Part C** will be a limited dose escalation part of the study evaluating the combination of trametinib with dabrafenib in children and adolescents with recurrent, refractory or unresectable BRAF V600 mutated tumors. This part of the study will establish recommended Phase 2 doses (RP2D) of dabrafenib and trametinib when given in combination in children and adolescents. This part of the study will enroll approximately 18 subjects (including up to 6 adolescent subjects with BRAF V600 mutant metastatic melanoma) and will not open to accrual until the dose of dabrafenib in children is established in study BRF116013, the dose of trametinib is established in Part A and review of the available safety and PK data of trametinib and dabrafenib monotherapy in children is completed. Amendment 3 provides the updated safety data and dabrafenib dosing in children. Parts B and C may be open to accrual simultaneously. Patients who have had prior dabrafenib therapy may enroll in part C if they have had prior benefit to dabrafenib monotherapy, as determined by the investigator.

**Part C extension** will be an age-specific dose exploration in 6 subjects aged 12 months to < 6 years old. If the trametinib dose of 0.032 mg/kg/day is tolerated in Part A extension, a combination of trametinib 0.032mg/kg/day and the full dabrafenib pediatric RP2D will be tested in this cohort. The goal of this additional dose exploration is to establish the safety, tolerability, PK and RP2D of the trametinib and dabrafenib combination in this younger age cohort

**Part D** will be a tumor cohort expansion part of the study to further evaluate the safety, tolerability, and preliminary clinical activity of the combination of trametinib and dabrafenib in tumor-specific pediatric populations listed below.

- D1: BRAF V600-mutant, relapsed or refractory low grade glioma (LGG)
- D2: BRAF V600-mutant, relapsed or refractory Langerhans cell histiocytosis (LCH)

Disease cohorts are selected based on current data of proto-oncogene RAS (Ras)/ mitogen-activated protein kinase (MAPK) activation in childhood solid tumors. Pediatric subjects 12 months to < 18 years of age are to be enrolled. Approximately 20 subjects with LGG and 10 subjects with LCH will be enrolled.

Subjects may not enroll in more than one part of the study. Subjects will receive study treatment until disease progression, death or unacceptable toxicity.

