#### ECG Data analysis

The number and percentage of patients with notable ECG values at scheduled assessments will be presented by Parts A, B, C, and D.

- QTcB
  - New value of  $> 450$  and  $\leq 480$  ms
  - New value of  $> 480$  and  $\leq 500$  ms
  - New value of  $> 500$  ms
  - Increase from Baseline of  $> 30$  ms to  $\leq 60$ ms
  - Increase from Baseline of  $> 60$  ms
- PR
  - Increase from baseline  $>25\%$  and to a value  $> 200$  ms
  - New value of  $> 200$  ms
- QRS
  - Increase from baseline  $>25\%$  and to a value  $> 120$  ms
  - New values of QRS  $> 120$  ms

The normal range for HR is displayed in [Table 2-7 Recommendation for normal heart rate per age group and gender](#). The number and percentage of patients with notable values will be presented.

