**Table 2-7 Recommendation for normal heart rate per age group and gender**

Age group	0-1 month	1-3 months	3-6 months	6-12 months	1-3 years	3-5 years	5-8 years	8-12 years	12-18 years
HR (bpm) Boys	(125, 190)	(125, 185)	(110, 165)	(105, 165)	(95, 155)	(75, 125)	(60, 115)	(55, 100)	(50, 100)
HR (bpm) Girls	(135, 215)	(125, 200)	(120, 190)	(105, 185)	(95, 180)	(80, 125)	(70, 115)	(60, 110)	(50, 100)

Data shown as upper limit of normal, lower limit of normal for HR= heart rate. Ref.: adapted from Rijnbeek et al. 2001.

The summaries will include all ECG assessments performed no later than 30 days after the last date of study drug. A listing of all ECG assessments will be provided and notable values will

be flagged. In the listing, the assessments collected outside of on-treatment period will be flagged.

The denominator to calculate percentages for each category is the number of patients with both a baseline and a post-baseline evaluation. A newly occurring post-baseline ECG notable value is defined as a post-baseline value that meets the criterion post-baseline but did not meet the criterion at baseline.

For each of the ECG parameter, descriptive statistics at baseline, at each post-baseline time point and changes from baseline at each post-baseline time point will be summarized. Descriptive statistics at worst post-baseline and changes from baseline to worst post-baseline will also be summarized separately. For each of the QTcB and QT intervals, shift tables based on notable parameter categories (<450, 450-<481, 481-<501, ≥501 ms) at baseline and the worst post-baseline value observed.

Patients with notable ECG interval values and newly occurring qualitative ECG abnormalities will be listed and the corresponding notable values and abnormality findings will be included in the listings.

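### The notable-value flags for blood pressure, weight, PR and QRS are not age-adjusted, so they mean little in the youngest children and flag normal growth

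*SAP*

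**What the plan says.** SAP Table 2-9 gives one high and one low criterion per vital sign, with no strata for age, sex or height.

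- Systolic pressure is notably high at "\geq 180$ with increase from baseline of $\geq 20" mmHg, that is, at least 180 with a rise of at least 20.
- Diastolic pressure is notably high at "\geq 105$ with increase from baseline of $\geq 15" mmHg.
- Weight is listed under the above-normal column at "increase $> 10\%$ from Baseline", with a mirror-image row for loss. No time limit is attached.

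In Section 2.8.4.1 (ECG Data analysis), PR and QRS each have two criteria: a rise above 25% that also ends above the absolute limit (200 ms or 120 ms), and a new value above that limit, as in "New values of QRS" above 120 ms. These are also unstratified, and the counts are presented by study part.

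Section 1.1 places infants in Part A and gives its extension "up to 12 subjects aged 1 month to < 6 years old". The Part C extension starts at 12 months, and for Part D "Pediatric subjects 12 months to < 18 years of age are to be enrolled".

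Elsewhere the SAP does adjust for age. Table 2-7, "Recommendation for normal heart rate per age group and gender", has nine age bands for boys and girls. Sections 5.1.4 and 5.3 match laboratory reference ranges to the age derived at each visit.

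**The concern.** A fixed limit can describe an abnormal value only if the normal range is roughly constant over the population. The SAP accepts that it is not constant for heart rate and laboratory values, but does not carry this over to blood pressure, PR, QRS or weight. Young children are a substantial part of the study: both extensions are restricted to under 6 years, and Section 3 plans 5 patients under 6 in each Part B cohort of at least 10.

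Section 2.5.1 makes ECG and vital signs part of the primary endpoint in Parts A to D. A very low count of notably high blood pressure could be read as reassurance when the rule could hardly fire in a small child. A high count of notable weight gain could be read as a drug effect when it reflects growth. Vital signs are tabulated by dose level or disease cohort and ECG flags by part, so ages are mixed in the same row and the reader cannot separate the two.

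**Working it through.** The SAP states no figure to reproduce here. The check applies its own rules to a range of starting values. The limits come from Table 2-9 and Section 2.8.4.1. The baselines and growth rates are assumptions, because the SAP gives none.

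**Systolic pressure.** Flag value = max(180, baseline + 20). The +20 condition matters only when baseline exceeds 180 − 20 = 160; below that the rule is simply 180 or more.

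**Diastolic pressure.** Flag value = max(105, baseline + 15). The +15 condition matters only above 105 − 15 = 90.

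| Sign | Assumed baseline (mmHg) | Rise needed (mmHg) |
|---|---|---|
| Systolic | 80 / 90 / 100 / 110 | 100 / 90 / 80 / 70 (125% / 100% / 80% / 64%) |
| Diastolic | 50 / 60 / 70 | 55 / 45 / 35 (110% / 75% / 50%) |

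**PR and QRS.** The combined criterion needs a value above max(200, 1.25 × baseline) for PR and max(120, 1.25 × baseline) for QRS. The 25% condition matters only above 200/1.25 = 160 ms and 120/1.25 = 96 ms. For a patient whose baseline is at or below the absolute limit, anything meeting the combined criterion also meets the new-value criterion. The 25% clause therefore adds no sensitivity there.

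- PR at assumed baselines of 100 / 120 ms: a rise of more than 100% / 67% is needed.
- QRS at assumed baselines of 60 / 70 / 80 ms: a rise of more than 100% / 71% / 50% is needed.
- For illustration, PR going from 100 to 190 ms (90/100 = +90%) or QRS from 60 to 115 ms (55/60 = +92%) is never notable.

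**Weight.** Months to +10% = 0.10 × baseline weight ÷ yearly gain × 12.

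| Baseline (kg) | Assumed gain (kg/year) | Months to +10% |
|---|---|---|
| 4 | 3 to 6 | 0.4/3 × 12 = 1.6 to 0.4/6 × 12 = 0.8 |
| 10 | 2 to 2.5 | 6.0 to 4.8 |
| 15 | 2 | 9.0 |
| 20 | 2 to 3 | 12.0 to 8.0 |
| 50 | 3 to 5 | 20.0 to 12.0 |

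The flag fires just after these times. A child with no gain has a change of 0% and meets neither weight row, however long treatment lasts.

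**Low blood pressure rows.** These limits (90 and 50 mmHg) are also unstratified, but they require a fall of at least 20 or 15 mmHg. A normally low infant value is therefore not flagged on its own.

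**The case against.** The strongest reply is that the cut-offs drive only one type of output. Section 2.8.5 also provides shift tables (categories not stated), descriptive statistics, change from baseline and a listing of all assessments. ECG parameters get change from baseline at each time point and at the worst value. Adverse events are CTCAE-graded and tabulated by age group under Section 2.8.1. No hypothesis is tested. This stands: a reader might infer that toxicity would be missed altogether, and the SAP does not support that.

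A reader might also infer that growth failure would go unseen. That does not follow either. The document history records SDS and velocity formulae in an Appendix 5.5, and the reference list cites a WHO growth reference that no visible section uses. A growth analysis may well sit in redacted text. Section 2.8.5.3 also lists growth-plate radiographs and Tanner staging. Only the inability of the Table 2-9 weight rows to flag a child who stops gaining can be held against the plan.

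Nor can it be assumed that every child is observed for 12 months. Section 1.1 ties that period to the last subject enrolled, apart from those who progress or withdraw, and it describes time in study. Vital signs are summarised on treatment, and the exposure bands in Section 2.4.1 start below 3 weeks. The weight result therefore applies to children who stay on treatment long enough.

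Finally, the SAP gives no source for the limits, so calling them adult values would be the reader's inference. None of this explains why heart rate and laboratory values are age-referenced and these four measures are not.

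**Conclusion.** The point holds for the notable-value counts and listing flags. The blood pressure, weight, PR and QRS criteria are fixed from infancy to 18 years, which is inconsistent with the SAP's own handling of heart rate and laboratory values.

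That the systolic rule reduces to 180 or more below a baseline of 160, and that the 25% clauses add no sensitivity for baselines within the absolute limits, follows from the SAP alone. The size of the effect rests on assumed values. A rise of 80 to 100 mmHg is needed at baselines of 80 to 100 mmHg. Ordinary growth crosses +10% in about 1 to 2 months at 4 kg and about 5 to 12 months at 10 to 20 kg. At 50 kg it takes 12 to 20 months, so the weight problem is mainly one of younger children on long treatment.

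Confidence is moderate, because the paediatric inputs are assumptions and part of the growth analysis may be redacted.

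**What to change.** Amend the statistical flags in Table 2-9 and Section 2.8.4.1 before database lock:

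- Replace the blood pressure rows with percentile categories referenced to age, sex and height.
- Replace the weight rows with change in weight-for-age SDS, aligned with the SDS formulae recorded in the document history, so that both excess gain and failure to gain can be flagged.
- Replace the PR and QRS limits with age-referenced upper limits.
- Name the paediatric reference source and the thresholds in advance; the choice is the sponsor's.

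The present rows can be kept as a secondary display for comparison with adult data. The change affects reporting flags only, not patient management.

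The cost is SAP wording and lookup tables. Height and weight are already collected (Section 2.8.5), sex and age are in the demographic data, and Section 5.1.4 already derives age by visit for laboratory data. The one downside is less direct comparability with adult programme tables, which the secondary display largely offsets.

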### **2.8.5.1 Karnofsky and Lansky Performance Status**

#### **Data handling**

The Karnofsky and Lansky PS scale (see Appendix 1) will be used to assess physical health of patients, ranging from 10 (least active) to 100 (most active).

#### **Data analysis**

Frequency counts and percentages of patients in each score category of 100, 90, 80, 70, and < 70 will be provided by cohorts and age groups at baseline and at each scheduled post-baseline visit. A patient will be reported only in the age group set at baseline. A summary of change from baseline by scheduled visits as well as the worst case post-baseline and the best case post-baseline changes during the study will be performed.

A supporting listing will also be provided.

### **2.8.5.2 Palatability**

Palatability assessments (bitterness, sweetness, texture and overall taste) will be listed for each patient receiving oral liquid formulation (i.e. trametinib solution or dabrafenib suspension) and summarized by assessment time. The number and percentages of patients for each category of palatability assessments will be summarized.

### **2.8.5.3 Physical Examination**

Dermatologic skin assessments, radiograph of wrist and tibial growth plate, and ophthalmologic examination will be listed for each patient at each time point.

In addition, tanner staging will be listed for each patient at each time point.

### **2.8.5.4 Cardiovascular Events**

Cardiovascular events will be listed for all patients in which an event occurred.

### **2.8.5.5 Pregnancies**

While pregnancy itself is not considered to be an AE or SAE, any pregnancy complication or elective termination of a pregnancy for medical reasons will be recorded as an AE or SAE as described in the protocol. If patients become pregnant while on the study, the information will be included in the narratives and no separate table or listing will be produced.

## 2.9 Pharmacokinetic endpoints

Pharmacokinetic analyses will be conducted based on the PK population unless otherwise specified.

### PK parameters

PK parameters for trametinib, dabrafenib and dabrafenib metabolites will be calculated based on non-compartmental methods using Phoenix WinNonlin version 5.2 or higher (Pharsight, Mountain View, CA). All calculations of non-compartmental parameters will be based on actual blood sampling times. PK parameters listed in Table 2-10 will be estimated and reported as data permit.

Population PK parameters may include the following and are dependent upon the final population PK model for both trametinib and/or dabrafenib: apparent clearance following oral dosing (CL/F), central volume of distribution (Vc/F), absorption rate constants (ka) and MTIME (time when absorption rate changes).

Final PK parameters will be summarized and will be compared to historical adult data.

**Table 2-10 PK parameters**

AUClast	The AUC from time zero to the last measurable plasma concentration sampling time (tlast) (ng*hr*mL  )
AUCtau	The AUC calculated to the end of a dosing interval (tau) at steady-state (after repeated dose). The plasma concentration at 12 or 24 hours after dosing will be set equal to the predose plasma concentration for the calculation of AUCtau
Cmax	The maximum (peak) observed plasma concentration following a single dose administration (ng/mL)
Tmax	The time to reach maximum (peak) plasma concentration following a single dose administration (hr)
CL/F	The total apparent body clearance of drug from plasma (L*hr  )
Ctrough	The observed plasma concentration just prior to the beginning of, or at the end, of a dosing interval
Cavg	The average steady-state plasma concentration will be calculated as the ratio of AUCtau (where tau = 24 h for trametinib and 12 h for dabrafenib), as data permit

For Part A and Part A extension, PK parameters will be summarized by day and dose level. Additionally, PK parameters will be summarized by age categories (<2 years, 2-<6 years, 6-<12 years, 12 to 18 years) for each dose cohort.

For Part B, PK parameters will be summarized by day, dose and disease cohort. Additionally, PK parameters will be summarized by age categories (<2 years, 2-<6 years, 6-<12 years, 12 to 18 years) for each disease cohort.

For Part C and C extension, PK parameters for trametinib, dabrafenib and dabrafenib metabolites will be summarized by day and combination regimen (e.g. TMT 0.0025mg/kg+DRB 2.25 mg/kg). Additionally, PK parameters will be summarized by age categories (<2 years, 2-<6 years, 6-<12 years, 12 to 18 years) for each combination regimen.

For Part D, PK parameters will be summarized by day, dose and disease cohort. Additionally, PK parameters will be summarized by age categories (<2 years, 2-<6 years, 6-<12 years, 12 to 18 years) for each disease cohort.

Descriptive statistics for trametinib, dabrafenib and dabrafenib metabolites (n, arithmetic mean, CV% mean, standard deviation (SD), median, geometric mean, CV% geo-mean, minimum and maximum) will be presented for all PK parameters, except Tmax, where only n, median, minimum and maximum will be presented.

All individual PK parameters will be listed by study part and treatment.

### **PK concentrations**

Descriptive statistics (n, m (number of non-zero concentrations), mean, CV% mean, SD, median, geometric mean, CV% geo-mean, minimum and maximum) will be presented for trametinib, dabrafenib and dabrafenib metabolite concentration at each scheduled time point by study part, day, and treatment dose .

Individual concentration-time profiles for trametinib, dabrafenib and dabrafenib metabolites with median will be displayed graphically by study part, day and treatment for All treated population on semi-log view. In addition, the median/geometric mean concentration-time profiles for trametinib, dabrafenib and dabrafenib metabolites will be displayed graphically by study part, day and treatment for PK population on linear and semi-log view.

All individual plasma trametinib, dabrafenib and dabrafenib metabolite concentrations will be listed by timepoint and summarized by study part, planned sampling time, treatment day and treatment.

[figure not shown]
